#### **6.2.1 Randomisation**

Patients will be randomly allocated to TA or placebo in a 1:1 ratio. Randomisation will be performed by central computer over the Internet using the eCRF. The investigators will record patient details via a secure web interface before randomisation takes place. Investigators may also contact the Trial Coordinating Centre via the 24-hours help-line.

The randomisation procedure will include a standard minimisation algorithm which will ensure that the treatment groups are balanced for key prognostic factors, such as sex, age, NIHSS score on admission and use of specific antidote treatment. To avoid predictable alternation of treatment allocation, and thus potential loss of allocation concealment, patients will be allocated with a probability of 0.80 to the treatment group that would minimise the difference between the groups on the key prognostic factors.

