### 11.4 Planned Analyses

Analysis will be by intention-to-treat; Missing outcome data will be imputed assuming worst possible outcome.

The primary outcome (HE) is to be compared between treatment and control arms adjusted for baseline volume using binary logistic regression. Although both baseline covariate adjusted and unadjusted results will be reported, baseline covariate adjusted analysis is prespecified as the primary outcome analysis for this trial.

As secondary outcome analyses, the proportions of mRS 0–4, mRS 0–3, and mortality outcomes will be compared between active and placebo arms of the trial adjusted for baseline volume using a binary logistic regression model. Analysis of the categorical shift in mRS will also be undertaken on the full range of the mRS using the Cochran–Mantel–Haenszel shift test and proportional odds logistic regression, subject to the validity of shift analysis model assumptions. Other secondary outcome analyses will be carried out according to standard statistical principles for comparison of parametric or nonparametric distributions as appropriate.

Exploratory analysis will be run on the primary and secondary outcomes, with adjustments for baseline

variables such as age, Glasgow coma scale (GCS), presence of IVH, and ICH location, and in the following subgroups: onset-to-treatment time (<six vs. >six-hours), baseline ICH volume (<30 vs. >30 ml), anatomical location (deep, lobar, or cerebellar), IVH (absent vs. present), GCS (>12 vs. 8–12), and age (<70 vs. >70), presence of spot-sign. These analyses will be hypothesis generating, as the trial is not powered for them.

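### Allocation is minimised on sex, age, NIHSS and antidote use, but the primary model adjusts only for baseline volume; if those factors predict hematoma expansion, the test is somewhat conservative and gives up some power

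*Combined protocol and SAP*

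**What the plan says.** Section 6.2.1 (Randomisation) describes a minimisation algorithm meant to keep the arms "balanced for key prognostic factors, such as sex, age, NIHSS score on admission and use of specific antidote treatment". It includes a random element: "patients will be allocated with a probability of 0.80 to the treatment group that would minimise the difference between the groups". The details are available in time for use as covariates: "The investigators will record patient details via a secure web interface before randomisation takes place".

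Section 11.4 (Planned Analyses) defines the primary comparison: "The primary outcome (HE) is to be compared between treatment and control arms adjusted for baseline volume using binary logistic regression". It ranks this above the unadjusted result: "baseline covariate adjusted analysis is prespecified as the primary outcome analysis for this trial". The binary mRS and mortality comparisons use the same single covariate: "mortality outcomes will be compared between active and placebo arms of the trial adjusted for baseline volume". Further adjustment is exploratory only, for "variables such as age, Glasgow coma scale (GCS), presence of IVH, and ICH location".

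The introduction to section 11 announces a detailed SAP, to be drawn up before the randomisation code is broken.

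**The concern.** The factors that drive allocation and the covariates in the analysis do not overlap. Baseline volume is in the primary model but is not a named minimisation factor. Of the four named factors, only age appears anywhere in 11.4, and only in exploratory work. Sex, NIHSS and antidote use appear in no listed model or subgroup, and no reason is given. The minimisation list is also open-ended, so the matching model terms cannot be read off the protocol.

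Minimisation makes the arms more alike on these factors than chance would. If the factors predict HE, the treatment estimate then varies less from trial to trial than the standard error of a model without them implies. The true type I error falls below 5%, and some power is given up relative to a model that contains them. At stake is efficiency, not validity.

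**Working it through.** **Inputs from the documents.** HE 54% on placebo and 27% on tranexamic acid, two-sided 0.05, 80% power, N = 109; interim at 82 patients, promising zone 0.33 to 0.8, cap 218, and an alternative rate of 35% on tranexamic acid (11.2); 1:1 minimisation with probability 0.80 on four factors (6.2.1); volume-only logistic model, and "Missing outcome data will be imputed assuming worst possible outcome" (11.4). The 5% dropout is stated in 11.2 only for the 218-patient case.

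**The plan's own figure.** With pooled variance, n per arm = [1.96·√(2·0.405·0.595) + 0.842·√(0.54·0.46 + 0.27·0.73)]² / 0.27² = (1.361 + 0.562)² / 0.0729 ≈ 51. That is 102 in total, and 102/0.95 ≈ 108, within one of the stated 109. Power at 109 is 82.8% with full data and 80.8% with 5% lost. The planned size is sound.

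**Assumed, because the documents are silent.** Odds ratios for HE (antidote; NIHSS per SD; age per SD; sex): weak 0.70, 1.2, 1.1, 1.1; moderate 0.41, 1.8, 1.35, 1.2; strong 0.25, 2.7, 1.65, 1.35. Volume odds ratio 1.5 per SD, 40% antidote use, 55% of one sex. Age and NIHSS are cut at the median for minimisation.

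**Planned adaptive design.** The Wald z at 82 patients gives conditional power for N = 109 under the current trend: Φ[(z/√t − 1.96)/√(1 − t)], with t = 82/109 = 0.75. If this lies in 0.33 to 0.8, N is raised to reach 0.8, up to 218. The final test is conventional, two-sided at 5%. In both arms 5% are missing and set to HE. There were 20,000 null and 10,000 alternative trials per case. Each cell gives volume-only vs factor-adjusted, in %:

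| Factors | Type I error | Power, 54 vs 27 | Power, 54 vs 35 |
|---|---|---|---|
| None | 5.1 vs 5.5 | 82.8 vs 83.0 | 52.4 vs 53.2 |
| Weak | 4.9 vs 5.5 | 83.0 vs 83.7 | 52.3 vs 53.6 |
| Moderate | 3.9 vs 5.1 | 83.5 vs 85.9 | 52.5 vs 57.6 |
| Strong | 3.2 vs 5.2 | 84.0 vs 89.2 | 53.0 vs 61.7 |

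At 54 vs 27 the gains are 0.2, 0.7, 2.4 and 5.2 points (paired SE 0.2 to 0.3). With an NIHSS–volume correlation of 0.5 they are 2.4 (moderate, 84.4 vs 86.8) and 4.4 (strong, 85.8 vs 90.2). With one predictive factor only, NIHSS at 1.8 gives 83.1 vs 85.0 and antidote at 0.41 gives 82.9 vs 83.9.

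**Is the gain only the slightly higher type I error?** At fixed N = 109 with full data and the adjusted test held to exactly 5%, power is 84.1 vs 83.8 (none), 83.9 vs 84.0 (weak), 84.8 vs 86.9 (moderate) and 85.8 vs 91.7 (strong). So there is no real gain in the first two cases, and a real gain in the last two.

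**Does the conservatism come from minimisation?** A separate simulation at fixed N = 109 used other assumptions: 25% antidote use, three NIHSS levels, and odds ratios for sex, age, NIHSS per level and antidote of 1.3, 1.3, 1.3, 0.7 (mild), 1.5, 1.5, 1.6, 0.5 (moderate) and 2, 2, 2.5, 0.33 (strong). For none to strong, volume-only type I error under minimisation was 4.7, 4.6, 4.0 and 3.2%; under simple randomisation it stayed at 4.8 to 5.1%. Adding the factors under minimisation gave 5.1 to 5.2%. Power was 84.5 vs 85.0, 84.4 vs 85.4, 85.2 vs 87.1 and 86.1 vs 90.7%.

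**Source of the gain.** In the moderate case the log odds ratio is −1.21 with SE 0.423 (volume-only) and −1.44 with SE 0.474 (adjusted). The ratios are 1.21/0.423 = 2.86 and 1.44/0.474 = 3.04. The interval is not narrower; the conditional effect is larger.

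**The case against.** The plan meets its promise without any change. Volume-only power exceeds 80% in every case of the adaptive design at 54% vs 27%, so the loss is only relative to a model the plan never proposed. That stands, and it keeps the point minor.

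The size rests on assumed effects. Section 6.2.1 calls the factors prognostic but does not say for HE. Under the assumptions the four factors alone have a c-statistic of 0.57 (weak), 0.70 (moderate) and 0.79 (strong), against about 0.59 to 0.61 for baseline volume. The two larger cases therefore make the omitted factors more predictive than the covariate the plan chose. This also stands: the benefit may be close to nil.

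A single-covariate model is a defensible choice with few events. Expected HE events are 109 × 0.405 ≈ 44 at the end and 82 × 0.405 ≈ 33 at the interim, or 33/6 = 5.5 per term with six terms. The adjusted Wald test ran at 5.1 to 5.6% in the adaptive design, though at 4.9 to 5.2% in a second, smaller run. Any excess is small but should be acknowledged.

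Mortality is sparser. At the 15 to 20% mentioned in the background, 109 patients give about 16 to 22 deaths. Six-term fits failed in 0 to 1% of simulated trials at 20% mortality and in 0.2 to 4.6% at 15% in one check, and in about 0.1 to 0.3% in another. A fallback should be named there.

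Finally, the exploratory covariate list is open, it includes GCS as a related severity measure, and the later SAP could add the factors. But nothing in the current text commits to that.

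**Conclusion.** The concern holds in its conditional form. The mismatch between allocation and analysis is plain from 6.2.1 and 11.4. If the factors predict HE, type I error of the volume-only test falls to about 3.9% (moderate) or 3.2% (strong). Power is then 2 to 3 or 4 to 6 points below that of a factor-adjusted model, at 54% vs 27% in the planned design. At 35% on tranexamic acid the gaps are wider: 57.6 − 52.5 = 5.1 and 61.7 − 53.0 = 8.7 points. If the factors are weak or irrelevant, the difference is under 1 point, and adjustment may cost up to about half a point.

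There is little slack in one setting. At fixed N = 109 with 5% imputed as HE, volume-only power is 79.3 to 79.9%, against 79.8 to 86.6% adjusted. These sizes depend on the assumed odds ratios, factor prevalences and cut-points. The direction does not, provided the factors carry information on HE. The change is worth making because it is cheap, not because the trial fails without it.

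**What to change.** In 11.4 and the SAP, before the 82-patient interim, define the primary logistic model as treatment, baseline ICH volume and the minimisation factors actually used: age and NIHSS as continuous terms, sex, and antidote use as recorded at randomisation. Use this one model for the interim conditional power and for the final test. In 6.2.1, replace the open-ended list with a closed one. Keep the volume-only and unadjusted models as supportive analyses. Use the same terms for the binary mRS and mortality models. Name a Firth penalised-likelihood fit as the fallback for separation or sparse data; it matters most for mortality.

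If the sponsor prefers volume only, the minimum is a stated reason and a prespecified factor-adjusted sensitivity analysis.

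The cost is a few sentences in 6.2.1, 11.4 and a SAP still to be drawn up, with no new data. The drawbacks are six terms on about 44 events (33 at the interim), a possible slight excess of type I error, a small power loss if the factors do not predict HE, and an odds ratio that is conditional on more covariates and has no narrower interval.

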## **12. QUALITY ASSURANCE AND CONTROL**

### **12.1 Data handling and record keeping / archiving**

All patients will be assigned a unique code number. The patient data will be linked to this number, and the patients' names or other personal identifiers will not be included in the database. The patient database will be kept on a separate, secure computer. The code will be stored on another, secure computer, and will be deleted 15 years after the results of the trial have been published. The trial's procedures for data protection will conform to the Swiss applicable regulatory requirements, and to the conditions set by the Swiss Data Inspectorate.

#### **12.1.1 Case Report Forms**

Patients' data will be collected using a web-based electronic case report form located at the Clinical Trial Unit in Basel. Case report forms will be filled in by local investigators.

#### **12.1.2 Specification of source documents**

Source data must be available at the site to document the existence of the study participants. Source data must include the original documents relating to the study, as well as the medical treatment and medical history of the participant.

#### **12.1.3 Record keeping / archiving**

All study data must be archived for a minimum of 10 years after study termination or premature termination of the clinical trial.

### **12.2 Monitoring**

During the course of the trial the Data Safety and Monitoring Board (DSMB) will after recruitment of 50% and 80% of the trial population perform an review of SAEs, in all patients; in case of concerns, unblinding will be requested. If, in their view, there is credible evidence of harm, or overwhelming evidence of efficacy, the committee will advise the CIs. Unless this happens, the CIs and the Steering Committee will remain ignorant of all interim results.

The DSMB will also be responsible for monitoring the overall conduct of the trial, and may formulate recommendations relating to the selection, recruitment, or retention of participants, or their management, or to improving their adherence to protocol-specified regimens, and the procedures for data management and quality control.

### **12.3 Audits and Inspections**

The study documentation and the source data/documents are accessible to auditors/inspectors (also CEC and CA) and questions are answered during inspections. All involved parties must keep the participant data strictly confidential.

### **12.4 Confidentiality, Data Protection**

Direct access to source documents will be permitted for purposes of monitoring, audits and inspections.

## **13. PUBLICATION AND DISSEMINATION POLICY**

The trial will be published in accordance with the CONSORT guidelines and will be presented by a writing committee on behalf of the investigators. All participating centres and collaborators will be acknowledged in the main publication. The primary results and results of any substudies will be presented at international meetings and in public media.

## **14. FUNDING AND SUPPORT**

This study is funded by a grant from the Swiss National Science Foundation (grant no: 32003B\_163378)

## **15. INSURANCE**

Insurance will be provided by the Sponsor. A copy of the certificate is filed in each investigator site file and the trial master file.

